7.1.1.6 Interruption duration

Study drug interruption duration will be calculated for each subject who experienced study drug interruption using the following:

Interruption duration (days) = End Date of Study Drug Interruption – Start Date of Study Drug Interruption + 1

If the Start Date of Study Drug Interruption or the End Date of Study Drug Interruption is missing, the first day of the month will be used.

If the date and month of the Start Date of Study Drug Interruption or the those of the End Date of Study Drug Interruption are missing, then the first day of the first month (January) will be used.

Drug Interruption : if all 3 investigational product tablets per day are not taken.

7.1.1.7 Duration of SSc-Interstitial lung disease (SSc-ILD)

Duration of SSc-ILD will be calculated for each subject using the following:

Duration of SSc-ILD (days) = The date of informed consent – The date of diagnosis of SSc-ILD + 1

7.1.2 Efficacy assessments

7.1.2.1 Primary Efficacy Endpoint

The primary efficacy endpoint is the ACR CRISS score which is a composite endpoint assessed in a 2-step process that calculates the probability of improvement for each subject ranging from 0.0 (no improvement) to 1.0 (marked improvement).

Step 1: Subjects who develop new or worsening of cardiopulmonary and/or renal involvement due to systemic sclerosis are considered as not improved (irrespective of improvement in other core items) and assigned a probability of improving equal to 0.0. Specifically, if a subject develops any of the following

- New scleroderma renal crisis (See protocol for definition)
- Decline in %pFVC $\geq 15\%$ (relative), confirmed by another %pFVC within a month, high resolution computer tomography (HRCT) to confirm ILD (if

previous high-resolution computer tomography of chest did not show ILD) and %pFVC below 80% predicted*

- New onset of left ventricular failure (defined as left ventricular ejection fraction $\leq 45\%$) requiring treatment*
- New onset of pulmonary arterial hypertension (PAH) on right heart catheterization requiring treatment.* PAH is defined as mean pulmonary artery pressure ≥ 20 mm Hg at rest and an end-expiratory pulmonary artery wedge pressure ≤ 15 mm Hg and a pulmonary vascular resistance > 3 Wood units

*= Attributable to systemic sclerosis.

The step 1 is up to medical judgement and the data in the CRF will be used directly for deriving the endpoint. If the data in the CRF is “NOT done” or “missing” then the ACR CRISS score will be missing.

Step 2: For the remaining subjects, Step 2 involves computing the predicted probability of improving for each subject using the following equation (equation to derive predicted probabilities from a logistic regression model):

$$\frac{\exp[-5.54 - 0.81 * \Delta_{MRSS} + 0.21 * \Delta_{FVC\%} - 0.40 * \Delta_{Pt-glob} - 0.44 * \Delta_{MD-glob} - 3.41 * \Delta_{HAQ-DI}]}{1 + \exp[-5.54 - 0.81 * \Delta_{MRSS} + 0.21 * \Delta_{FVC\%} - 0.40 * \Delta_{Pt-glob} - 0.44 * \Delta_{MD-glob} - 3.41 * \Delta_{HAQ-DI}]}$$

where Δ_{MRSS} indicates the change in MRSS from baseline to each visit, $\Delta_{FVC\%}$ denotes the change in FVC% predicted from baseline to each visit, $\Delta_{Pt-glob}$ indicates the change in subject global assessment, $\Delta_{MD-glob}$ denotes the change in physician global assessment, and Δ_{HAQ-DI} is the change in HAQ-DI. All changes are absolute change (Time₂–Time_{baseline}).

At the Investigator’s discretion, if a subject’s medical conditions are worsening such as %pFVC decline, an HRCT scan may be performed as a part of standard of care based on a local guidance to confirm worsening.

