6 INTRODUCTION

MT-7117 (dersimelagon) is a novel orally-administered, small molecule, which acts as an agonist of melanocortin-1 receptor (MC1R) and is being developed by Mitsubishi Tanabe Pharma to reduce active inflammatory and fibrotic processes in adults with diffuse cutaneous systemic sclerosis (dcSSc).

MC1R is a member of the G-protein-coupled receptors superfamily. It is the predominant melanocortin receptor expressed in cutaneous and hair follicle melanocytes. MC1R is activated by α -melanocyte-stimulating hormone which can be locally synthesized in response to sunlight exposure. MC1R regulates the amount and type of pigment production and is a major determinant of skin phenotype and sensitivity to ultraviolet light induced damage.¹ MC1R has also been reported to be expressed by a variety of cell types, including fibroblasts, endothelial cells, and immune cells.² Activation of MC1R enhances deoxyribonucleic acid (DNA) repair, upregulates antioxidant enzymes, and reduces production of proinflammatory cytokines,³ suggesting that MC1R is important for the resolution of inflammation.⁴ Therefore, agonism of MC1R is associated not only with increased skin pigmentation, but also with regulation of inflammatory responses.^{1,4,5}

Systemic sclerosis (SSc) is a complex polygenic, autoimmune, and chronic medical condition characterized by excessive production of collagen (fibrosis), microvascular damage in the skin, joints, lung, esophagus, gastrointestinal tract, kidneys, heart, and other internal organs⁶, with an estimated prevalence in the United States (US) of 276-300 cases per million with an incidence of about 20 cases per million per year.^{7,8} The 10-year survival has reportedly improved from the 1970s (54%–60%) to the 1990s (66%–78%).⁸

The patient population is highly heterogeneous, with each patient presenting with unique combinations of organ involvement, symptoms, and progression. There are 2 major recognized patterns that the illness can take: diffuse or limited disease. In diffuse scleroderma, skin thickening occurs more rapidly and involves more skin areas than in limited disease. In addition, subjects with diffuse sclerosis have a higher risk of developing “sclerosis” (fibrous hardening) of the internal organs.⁶

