5.2 Intent-to-Treatment (ITT) Population

The Intent to treat (ITT) population includes all randomized subjects who receive at least 1 dose of study drug. The ITT population will be used for all efficacy analyses. The subject randomized treatment will be used for efficacy analyses.

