5.3 Per-protocol (PP) population

The per-protocol population includes all ITT subjects who do not have to be excluded due to relevant protocol deviations (to be discussed in the blinded data review meeting) and who complete Week 52 (the end of double blinded treatment period). The PP will be used to perform supportive analysis for the only primary endpoint (CRISS).

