8.2.1 Primary Efficacy Endpoint

Primary Analysis

The primary treatment comparisons of interest are the ACR CRISS score for MT-7117 treatment group compared with placebo group at Week 52. MT-7117 treatment group includes all subjects treated with MT-7117 regardless down titrated or not. The treatment MT-7117 dose level at EOT will be compared with placebo as secondary analysis.

The primary endpoint will be summarized using descriptive statistics with interquartile range. The distribution of ACR CRISS score may not be normal distribution. For ACR CRISS score at Weeks 16, 26, 39, and 52 the comparison between MT-7117 treatment group and placebo group will be performed using the non-parametric analysis method. The point estimates and 2 sided 95% CIs and associated P-values for the difference between the treatment groups will be obtained using the Hodges-Lehman estimator corresponding to Wilcoxon's rank sum test. This non-parametric analysis will be performed with multiple imputation method, assuming missing at random. A supportive analysis will be performed at the same way for the primary endpoints using the per-protocol set (PPS). As a secondary analysis for the primary endpoint, the same analysis method will be applied to the intent to treat (ITT) population but the patients' data after taking rescue therapy will not be included. This approach will be performed to investigate a sensitivity for the primary analysis.

MI Step 1: The ACR CRISS score at week 52 will be multiply imputed using Fully Conditional Specification Method methodology under MAR assumption. The imputation for the missing ACR CRISS total score at week 52 will be conducted using all visit data of all subjects with available ACR CRISS total score up to week 52. The 50 different imputed datasets will be created using the MI procedure in SAS with 2023 for seed value. The following factors will be included in the imputation model: treatment group (TRT01P), randomization strata (the baseline autoantibody status of anti-RNA Polymerase III (positive or negative)).

[REDACTED]

[REDACTED]

[REDACTED]

[REDACTED]

[REDACTED]

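### No visible rule gives the primary CRISS score a value after death, so a death before Week 52 is imputed near the arm mean although new organ failure scores 0.0

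*SAP*

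**What the plan says.** SAP 7.1.2.1 builds the primary score in two steps. In Step 1, subjects who develop scleroderma renal crisis, a confirmed relative %pFVC decline of at least 15%, left ventricular failure or pulmonary arterial hypertension "are considered as not improved (irrespective of improvement in other core items) and assigned a probability of improving equal to 0.0". Step 2 applies the logistic equation to everyone else. Step 1 status is taken directly from the CRF, and if that entry is not done or missing, "then the ACR CRISS score will be missing".

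The analysis set is defined in SAP 5.2: "The Intent to treat (ITT) population includes all randomized subjects who receive at least 1 dose of study drug". SAP 8.2.1 fills the gaps: "The ACR CRISS score at week 52 will be multiply imputed using Fully Conditional Specification Method methodology under MAR assumption". On the predictors it says: "The following factors will be included in the imputation model: treatment group (TRT01P), randomization strata". It also uses CRISS scores from all visits, and it states that the imputed datasets hold no missing values. The lines that follow the predictors, and the SAS code, are redacted.

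Death appears in the visible text only under safety reporting (SAP 8.3.1). Protocol 16.3.4.2 did count empty Week 52 data as non-improvement, but only for the CRISS improvement proportion, and SAP 10 removes that analysis from the secondary endpoints.

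**The concern.** The endpoint's own logic is that serious organ failure is the worst result whatever the other components show. Death is at least as bad. Yet on the visible text it is handled as ordinary missing data, and the subject enters the primary comparison with a drawn score well above 0, higher on the better arm.

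A lesser version affects Step 1. The rule that turns an empty CRF entry into a missing score has no exception for an organ event recorded earlier. A subject with such an event and an empty Week 52 could therefore also be imputed above 0.

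Neither planned supporting analysis would show the effect. The per-protocol set requires completion of Week 52 (SAP 5.3), so it drops these subjects. For the analysis without post-rescue data, "the same analysis method will be applied to the intent to treat (ITT) population", so the same MAR imputation applies.

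**Working it through.** **The plan's own figure, as a yardstick.** SAP 3.3 gives 72 subjects, difference 0.35, SD 0.5, two-sided 0.05, 80% power. For a rank-sum test with normal shift, P(X>Y) = Φ(0.35/(0.5√2)) = 0.690. Then N = (1.960 + 0.842)² / (12 × 0.25 × 0.190²) ≈ 72.7, and power at N = 72 is 79.6%. The figure reproduces and is not in dispute.

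**Path of a death through the rules.**
1. Death is not a Step 1 criterion (SAP 7.1.2.1), so no 0.0 is assigned.
2. No Week 52 CRF entry or components exist, so the score is missing.
3. The subject was dosed, so remains in ITT (SAP 5.2).
4. MI replaces the missing score with draws that depend on arm, stratum and any earlier CRISS scores (SAP 8.2.1).

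**Path of a Step 1 event with an empty Week 52.** The SAP 7.2 window for the CRISS components at Week 52 is Day 320 to 379, and that table has no early-termination row. An early-termination visit before Day 320 falls in an earlier window (Day 229 to 319 is Week 39), so Week 52 stays empty. By default SAP 7.2 does not fill a visit from outside its window.

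**How many deaths.** The documents give no trial death rate. Protocol 6 quotes 10-year SSc survival of 66% to 78% for the 1990s. Assuming constant hazard, expected deaths per arm in one year are 36 × (1 − S^(1/10)):
- S = 0.78: 36 × 0.0245 = 0.88
- S = 0.66: 36 × 0.0407 = 1.47

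With Poisson counts and equal hazards, the chance of two deaths on MT-7117 and none on placebo is (λ²/2)·exp(−2λ). This is 6.7% at λ = 0.88 and 5.7% at λ = 1.47, and the reverse split is equally likely. If both deaths must precede the first CRISS visit (Day 78 to 113), it is 1% to 4%.

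**Size on the mean scale.** Assume arm means of 0.675 and 0.325 (difference 0.35). Moving one MT-7117 subject from 0 to the arm mean adds 0.675/36 = 0.019. One death per arm adds (0.675 − 0.325)/36 = 0.010. Two on MT-7117 add 0.038, and two on placebo subtract 2 × 0.325/36 = 0.018.

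**Size on the planned estimator, by simulation.** Scores come from the SAP Step 2 equation with 36 per arm. Assumed inputs:
- SDs of change: mRSS 6, %pFVC 4.8, each global assessment 2, HAQ-DI 0.45
- between-component correlation 0.3
- Week 52 mean CRISS (placebo/MT-7117) 0.30/0.65, 0.40/0.60, or 0.45/0.45 (no effect)
- regression imputation on arm, stratum and earlier scores.

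An early death (no post-baseline CRISS) is imputed on average at 0.59 to 0.66 on MT-7117 and 0.29 to 0.42 on placebo. The change in Hodges-Lehmann shift, plan minus zeros, is:

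| Early deaths, MT-7117/placebo | Change | Example at true mean difference 0.35: plan v zeros |
|---|---|---|
| 1/1 | about +0.02 to +0.03 | 0.377 v 0.350 |
| 2/0 | +0.04 to +0.08 | 0.368 v 0.290 |
| 0/2 | -0.03 to -0.015 | 0.337 v 0.363 |

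With no true effect the change is at most about 0.017 either way.

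Later deaths give similar sizes. If those who die after Week 26 come from the lower half of Week 26 scores, the change is +0.017 to +0.025 at 1/1 and +0.040 to +0.065 at 2/0.

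A Step 1 zero recorded at Week 26 followed by an empty Week 52 matters less, because the zero is itself a predictor: +0.012 to +0.022 at 1/1 and +0.028 to +0.062 at 2/0.

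**The case against.** **Step 1 already reads as a by-subject rule.** It speaks of subjects who develop an event, and Step 2 covers only those who remain. On that reading a recorded renal crisis stays at 0.0, and the empty-entry sentence is meant for subjects whose status is unknown. This is the more natural reading and it stands. A reader might infer that organ failures will routinely be imputed away, and the documents do not support that. Subjects who stop drug are encouraged to complete Week 52 (Protocol 9.5), every attempt is made to obtain an early-termination visit, and such a visit from Day 320 falls in the Week 52 window. What remains is an early termination before Day 320, where the sentence as written has no exception.

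**A rule may exist out of sight.** Text directly after the imputation factors is redacted, and SAP 7 lets the blinded data review meeting depart from the conventions. This stands too, and it limits the claim to visible text. A decision at that meeting would still not be a rule stated in the plan.

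**The effect is small.** Eligibility excludes FVC at or below 50% predicted, significant pulmonary hypertension, ejection fraction below 45% and recent renal crisis, so the historical SSc death rate may be too high. Early diffuse disease may push the other way. At one death per arm the change is small beside the planned 0.35, and more lopsided splits than two to none are improbable at this rate. This is accepted.

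**Scoring every death 0.0 is a choice.** Three of the four Step 1 criteria require attribution to SSc, so counting only attributable deaths is also defensible. That is why the fix carries a sensitivity analysis.

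**Conclusion.** The point on death holds for the visible text: following SAP 5.2, 7.1.2.1 and 8.2.1 as written gives a subject who died a score centred on the subject's own arm, while the same plan scores new organ failure 0.0. The Step 1 point is a lesser one, a missing clarification that matters only when Week 52 is empty.

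The likely effect on the estimate is small. The sizes rest on assumed component distributions, an assumed imputation model and a historical death rate. The documents give no trial death rate and no Step 1 event rate.

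Two stronger inferences are not supported. The gap does not always favour the drug, since deaths on placebo move the estimate the other way. Nor is there a basis for a claim on type I error or power: with no true effect the shift barely moves, and the actual imputation code is not visible. The point is worth fixing because it concerns the definition of the primary endpoint and the repair is cheap.

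**What to change.** Add two rules to SAP 7.1.2.1, applied before imputation:

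1. *Once a Step 1 event is recorded, CRISS is 0.0 at that and every later analysis visit, including Week 52, even if later Step 1 entries or components are missing; these values are not imputed.*
2. *Death before Week 52 is set to 0.0 and not imputed.* Add one sensitivity analysis that handles deaths not attributable to SSc as the current plan does.

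The cost is two sentences and one extra run, with no new data collection. The downside is that deaths unrelated to SSc count as failures in the primary analysis, which the sensitivity analysis addresses, and that there are a few more ties at 0. If a redacted line already contains such a rule, stating it in 7.1.2.1 costs almost nothing.

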7.1.2.2 Secondary Efficacy Endpoints

- ACR CRISS Responder

An ACR CRISS score of 0.60 or greater indicates that a subject improved on treatment and a score of less than 0.6 suggests that a subject has not improved.

- HAQ-DI

The HAQ-DI is a self-administered instrument that measures physical disability in 8 different domains of function: dressing/grooming, arising, eating, walking, hygiene,

reach, grip, and common activities. Subjects are asked about 2 or 3 activities associated with each category and choose whether they are able to perform the activity ‘without any difficulty’, ‘with some difficulty’, ‘with much difficulty’, or ‘unable to do’. An additional section asks subjects to indicate if they used any aids or devices or needed assistance to perform daily activities.

A negative change from baseline indicates improvement. The Minimal Clinically Important Difference (MCID) for improvement ranges from 0.14-0.22 (Khanna et al. 2006; Pope 2011)

HAQ-DI is calculated based on the following points.

- There are four possible response for each component:
 - Without ANY difficulty = 0
 - With SOME difficulty = 1
 - With MUCH difficulty = 2
 - UNABLE to do = 3
- A category score is determined from the highest score of the components in that category (except when aids and devices are taken into account; see below). For example, if there are three components in a category and the responses were 1, 2 and 0 to the components in the category, then the score for the category would be 2.
- If a category consists of only two questions
- and has one missing response, then the non-missing response will be used as the value for the category. If a category consists of three questions and has one missing response, then the category score will be the higher of the two responses. If a category consists of three questions and has two missing responses, then the category will be considered missing.
- To calculate the HAQ-DI, the patient must have a category score for at least six of the eight categories. The HAQ-DI is the sum of the category scores, divided by the number of categories that have a score.
- The HAQ-DI takes into account the patient’s use of aids or devices in the scoring for a category. For each of the eight categories, there is an aids or devices companion variable(s) that is used to record any assistance the patient uses. Where aids or devices are indicated by a patient for a category or help from another person is required for a category, if the maximum score for the category is <2 , the category score is increased to 2 to reflect the use of an aid or device, or help. If the maximum value is ≥ 2 , the score is not modified. In the event that a category score is missing

but a corresponding aid or device is listed, then the score for that category will reflect the use of the aid or device (i.e., it will be scored as 2).

- Where “other” is ticked for use of aids or devices, the use of the aid or device will not be assigned to a category and will therefore not be reflected in the category scoring.
- If there are fewer than 6 categories with responses, an HAQ-DI cannot be calculated.
- The assignment of aids and devices to categories is done as follows:

Aid or device	Associated with category
Cane, walker, crutches, wheelchair	Walking
Devices used for dressing	Dressing and grooming
Built up or special utensils	Eating
Special or built up chair	Arising
Raised toilet seat	Hygiene
Bath tub seat	Hygiene
Jar opener (for jars previously opened)	Grip
Bath tub bar	Hygiene
Long-handled appliances for reach	Reach
Long-handled appliances for bathroom	Hygiene

- No aids or devices are assigned to the category ‘Activities’.
- Help from another person for errands and chores is assigned to the category ‘Activities’.
- Patient Global Assessment
The Patient Global Assessment is used to assess the subject’s rating of their overall disease activity. Subjects rate their perceived health on an 11-point scale from 0 (excellent) to 10 (extremely poor).
A negative change from baseline indicates improvement. The MCID has been reported by Sekhon and Pope 2010 to be -6.70 mm on Global VAS scale 100 mm. Therefore, -0.67 point will be defined as MCID in this assessment.
- Observed FVC and %pFVC
Pulmonary function tests (PFTs) are a group of tests that measure how well the lungs are performing. The test includes how well the subject is able to breathe and how effective the lungs are able to bring oxygen to the rest of the body. PFT evaluators need to be trained and appropriately qualified to perform both Spirometry and DLco tests.

FVC measurements will be conducted in the clinical site at around the same time of day where possible with the subject in a sitting upright position. Subjects should undertake at least 3 attempts to generate acceptable and reproducible FVC data per ATS/ERS guidelines. The highest acceptable value will be selected following quality review by a centralized over read specialist in agreement with the site Investigator. Single-breath DLco will be performed at selected sites/countries in accordance with recently published ATS/ERS (the American Thoracic Society/European Respiratory Society) guidelines using equipment and testing techniques that meet ATS/ERS requirement. At least 2 acceptable tests that meet repeatability criteria will be performed. The best value (mean from acceptable values) will be selected by a centralized over read specialist in agreement with the site Investigator.

The acceptability of the FVC and DLco data will be determined by a centralized over read specialist. The centralized over read specialist will state whether a session has been accepted (passed QA) or rejected (failed QA). As the lungs are involved in most of dcSSc patients, there is some difficulties for dcSSc patient to repeat PFTs until they have acceptable values to meet the ATS/ERS criteria. Even if there was no accepted (passed QA) value at each visit, we accept that value as long as there is no issue with the flow loop legibility, since, for some dcSSc subjects, this is their best performance. Records of such manoeuvres should be retained since they may contain useful information. The QA passed values will be used at each visit unless there is no acceptable values at a visit.

PFTs data will include observed FVC, %predicted FVC, observed DLco, and %predicted DLco such as below.

- 1) Observed FVC is the best FVC and the highest FVC value from accepted values.
- 2) FEV is the forced expiratory volume in one second, which is the volume delivered in the first second of the best FVC manoeuvre..
- 3) %pFVC is the best FVC as a percentage of predicted FVC (Best FVC/pFVC x 100%).
- 4) Observed DLco is the best DLco uncorrected for Hb diffusing capacity of the lung for carbon monoxide in mLCO/min/mmHg.
- 5) %pDLco is the uncorrected best DLco as a percentage of corrected predicted DLco for hemoglobin (Best DLco/pDLco x 100%).

- Physician Global Assessment

The Physician Global Assessment is used to assess the physician's rating of overall health of the subject. Physicians rate the perceived health of the subject on an 11 point

scale from 0 (excellent) to 10 (extremely poor). Higher scores indicate worse disease in terms of severity, damage, or overall disease, but there is no standardization for the scale (Pope 2011). A negative change from baseline indicates improvement. Expert consensus has suggested a range of 8-13 units on Global VAS scale 100 mm. for the MCID (Gazi et al. 2007). Therefore, -0.8 to -1.3 points will be defined as MCID in this assessment.

- Modified Rodnan Skin Score (MRSS)

The mRSS will be assessed by a qualified and trained Efficacy Assessor to limit the variability. The same Efficacy Assessor will measure skin thickness on 17 different body areas on a scale from 0 (normal) to 3 (severe). Global average scoring method (The assessor scores individual sub-areas, as needed for differences within large areas and takes average of sub-areas to attain the score for that overall area) will be used as a scoring technique in this study. Worsening of skin fibrosis as measured by the mRSS score was associated with a disease progression and overall mortality in subjects with dcSSc, indicating that the mRSS is a good surrogate marker for disease progression. The mRSS is a measure of skin thickness across 17 different body sites and has a range of 0 to 51 in whole units. Total score is derived from the sum of the 17 different body areas. If at least one domain score is missing, the total score will be regarded as missing. The MCID has been reported by Dinesh Khanna 2019 to be 3 to 5 units for dcSSc patients.

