11.10 Patient Reported Outcomes

To minimize bias, subjects will be assured that all data will be treated confidentially, and the answers will not have any influence on study drug treatment. Unless otherwise noted (e.g., Investigator or designee to complete questionnaire), subjects will complete the questionnaires on their own, or with the help of relatives, friends or study staff if restricted by digital lesions, and it is also desirable that subjects complete those before being seen by the clinician at the respective visit. Subsequently, a member of the site Investigator's team will enter the responses into the eCRF.

All PROs will be completed at the times described in Table 1.

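### The HAQ-DI missing-item rule in SAP 7.1.2.2 discards a category score that a lone answer of 3 already fixes (minor)

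*SAP*

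**What the plan says.** SAP 7.1.2.2 scores each HAQ-DI item from 0 to 3, with 3 meaning the subject cannot do the activity. "A category score is determined from the highest score of the components in that category".

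The rules for blank items depend on the number of questions in the category:

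- Two questions, one blank: the category stands, because where it has two questions "and has one missing response, then the non-missing response will be used as the value for the category".
- Three questions, one blank: "If a category consists of three questions and has one missing response, then the category score will be the higher of the two responses".
- Three questions, two blank: "If a category consists of three questions and has two missing responses, then the category will be considered missing".

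The bullet on aids and devices lifts a category maximum below 2 to 2 and leaves a maximum of 2 or more alone. It then adds that where a category has been left unscored "but a corresponding aid or device is listed, then the score for that category will reflect the use of the aid or device", and gives that score as 2. For the index itself, "The HAQ-DI is the sum of the category scores, divided by the number of categories that have a score", provided at least six of the eight categories are scored.

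The questionnaire in Protocol Appendix 6 has three questions in Eating, Hygiene, Grip and Activities and two in each of the other four categories. The SAP assigns no aid or device to Activities.

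HAQ-DI change from baseline is a secondary endpoint (SAP 2.2.2). It also enters Step 2 of the CRISS score with coefficient −3.41 (SAP 7.1.2.1).

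**The concern.** A maximum cannot exceed the top of its scale. If one of three items is answered 3 and the other two are blank, the blanks could not have changed the category score. Nothing needs imputing, yet the rule throws the value away and averages over the remaining categories.

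The rule also disagrees with its neighbours. A lone 3 counts as 3 in Walking but is voided in Eating. The pattern (3, 0, blank) scores 3, but (3, blank, blank) is missing. If a device is listed, the missing-category sentence gives 2 to a subject who answered 3, while the sentence just before it protects maxima of 2 or more. Two programmers could code this differently.

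At stake is the accuracy of individual values in the HAQ-DI change endpoint, in the CRISS score, and in responder status at the 0.6 cut-off.

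**Working it through.** **Inputs.** From SAP 7.1.2.2: item range 0–3, highest-response rule, missing-item rules, device rule, six-category minimum, mean of scored categories, and a minimal clinically important difference (MCID) for improvement of 0.14–0.22. From SAP 7.1.2.1: coefficient −3.41, applied to visit minus baseline. The documents give no rate of item non-response.

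**The SAP's own example.** Responses 1, 2 and 0 give max(1, 2, 0) = 2, as the SAP states.

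**The rules applied as written.**

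| Responses | No device | Device listed |
|---|---|---|
| 3, blank (two-question category) | 3 | 3 |
| 3, 0, blank | 3 | 3 |
| 3, blank, blank | missing | 2 |

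Only the last row departs from the known maximum. For a lone answer of 0, 1 or 2 with a device, the result of 2 matches what the ordinary device rule would give, so the device sentence goes wrong only for a lone 3.

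**Loss without a device.** Let the other seven categories all be scored, with mean m. Keeping the 3 gives (7m + 3)/8. Voiding it gives m. The loss is (7m + 3)/8 − m = (3 − m)/8. Since m cannot exceed 3, the loss is never negative. Checking all 4^7 combinations of the other seven scores confirms this. The CRISS logit shift is 3.41 times the loss.

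| m | HAQ-DI voided | HAQ-DI with 3 kept | Loss | CRISS logit shift |
|---|---|---|---|---|
| 0 | 0 | 0.375 | 0.375 | 1.28 |
| 0.5 | 0.5 | 0.8125 | 0.3125 | 1.07 |
| 1 | 1 | 1.25 | 0.25 | 0.85 |
| 1.5 | 1.5 | 1.6875 | 0.1875 | 0.64 |
| 2 | 2 | 2.125 | 0.125 | 0.43 |
| 2.5 | 2.5 | 2.5625 | 0.0625 | 0.21 |
| 3 | 3 | 3 | 0 | 0 |

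The loss drops below the lower MCID figure of 0.14 once m exceeds 3 − 8 × 0.14 = 1.88.

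**Loss with a device (literal reading).** (7m + 3)/8 − (7m + 2)/8 = 1/8 = 0.125 for any m, a logit shift of 3.41 × 0.125 = 0.43. This is just below the MCID range.

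**Six-category limit.** Take five other categories scored at 1 and two others missing. Keeping the 3 gives (5 + 3)/6 = 1.33. Voiding it leaves five scored categories, so HAQ-DI is missing. CRISS Step 2 then lacks an input, and at Week 52 the score passes to imputation.

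**Direction in the endpoints.** Take a true CRISS of 0.50 (logit 0) and, for the no-device case, m = 1:

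- Occurrence at the follow-up visit: 1/(1 + e^−0.85) = 0.70 without a device, 1/(1 + e^−0.43) = 0.605 with one. Both cross 0.6.
- Occurrence at baseline: 0.30 and 0.395. A baseline occurrence carries into the change at every later visit.

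These examples lie near the cut-off. For a follow-up occurrence at m = 1, only true scores from about 0.39 up to 0.60 cross it.

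**Frequency, by assumption only.** Over baseline and four visits there are 72 × 5 × 4 = 1,440 three-question category scores. The Week 52 score draws directly on 72 × 2 × 4 = 576. If 1% of these had two blanks and 10% of the lone answers were 3, the joint rate would be 0.1%: about 1.4 wrong category scores over all visits and 0.6 in the Week 52 inputs. A joint rate of 1% would give about 14 of 1,440.

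**Effect on the primary test.** Suppose one subject moves from 0.45 to 0.66 and the scores in the other arm are roughly uniform (assumed). The Mann–Whitney count changes by about 0.21 × 36 = 7.6 of 36 × 36 = 1,296 pairs. Its null SD is √(36 × 36 × 73/12) = 88.8, so z moves by about 0.09.

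**The case against.** The strongest reply is that this hardly matters. A wrong score needs exactly two of three items blank and the third answered 3. The documents give no sign that this is common. Later entry by site staff ("team will enter the responses into the eCRF") does not show that blanks occur, subjects may be helped with the form, and Protocol 15.2 provides for completeness review of the eCRF. SAP section 7 also lets the blinded data review override its conventions. The primary comparison is rank-based, and one affected subject barely moves it. All of this stands, and it is why the point is minor.

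The device result of 2 is one reading of two conflicting sentences. A programmer could take the protection of maxima of 2 or more as covering the lone 3. That also stands; the remedy is to reconcile the sentences. The missing-category device route cannot reach Activities at all.

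SAP section 12 lists published HAQ-DI scoring instructions, which were not available here. Whether the rule follows them is unknown. Either way, the conflict inside the SAP remains.

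A reader might infer that the rule always understates disability, or that it biases the treatment effect. The documents support neither. The no-device loss is zero when every other scored category is 3, and HAQ-DI may become missing rather than lower. Both endpoints use change from baseline, so the direction depends on the visit affected. The same rule applies to both arms under blinding, and nothing suggests that the blanks differ by arm.

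**Conclusion.** The defect is real but small. In four of the eight categories the SAP discards a score that its own highest-response rule fixes at 3. In three of those, the literal device sentence replaces it with 2.

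Per occurrence, with all other categories scored, HAQ-DI at that visit is lowered by (3 − m)/8 without a device or by 0.125 with one; it is never raised. At m = 1 the no-device loss of 0.25 exceeds the SAP's quoted MCID range and can change an individual's responder status near 0.6. The two losses rest only on the SAP's scoring rules. The 0.125 also rests on the literal reading of the device sentence.

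The effect on the trial result is expected to be small. That judgement rests on the pattern being uncommon, which the documents neither confirm nor deny.

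**What to change.** Add two sentences to the HAQ-DI rules in SAP 7.1.2.2 before database lock:

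1. A category is scored 3 whenever any answered item in it is 3, however many other items are blank.
2. The rule that scores a missing category 2 when a device is listed applies only if no answered item in that category is 3.

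Leave two things as they are. An all-blank category with only help from another person ticked should stay missing, since the missing-category sentence names aids and devices only. Lone answers of 0 to 2 in three-question categories should also keep their present handling, because there the maximum is not known and accepting a lone 0 could itself understate disability.

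The cost is two sentences and about one line of derivation code. No assumption about unanswered items is added.
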